9.2.5 SAEs (Including Deaths) and Adverse Events Leading to Study Drug Discontinuation

SAEs (including deaths) and AEs leading to study drug discontinuation will be summarized by SOC and PT and in listing format.

9.2.6 Adverse Events of Special Interest

Adverse events of special interest (AESI) through Week 24, through Week 48 and through Week 48 per 100 patient-years will be summarized by SOC and PT. AESI will also be provided in listing format. It will be identified based on standardized or company MedDRA queries (SMQs or CMQs specified in [Appendix B](#)).

9.2.7 Adverse Events by "Reasonably Possibly Related" Relationship

TEAEs and reasonably possibly related AEs through Week 24, through Week 48 and through Week 48 per 100 patient-years occurring for more than 2% of the subjects in any of the treatment groups will also be summarized by MedDRA SOC and PT. If a subject has an AE with an unknown relationship, then the subject will be counted in as 'related.'

9.2.8 Frequent (> 5%) Adverse Events and Reasonably Possibly Related Adverse Events by Preferred Term in Decreasing Frequency

TEAEs and reasonably possibly related AEs through Week 24, through Week 48 and through Week 48 per 100 patient-years occurring for more than 5% of the subjects in any of the treatment groups will be summarized by MedDRA PT in decreasing frequency separately.

9.2.9 Listing of Adverse Events

The following additional summaries of AEs will be prepared.

- Listing of Subjects with Treatment-Emergent AESIs.
- Listing of Subjects with Pretreatment SAEs.
- Listing of Subjects with Treatment-Emergent SAEs.
- Listing of Treatment-Emergent AEs that led to discontinuation of study drug.
- Listing of all deaths.

9.3 Analysis of Laboratory Data

Data collected from central and local laboratories, including additional laboratory testing due to an SAE, will be used in all analyses, except for baseline, where SAE-related laboratory assessments on or before the first dose of study drug will be excluded. The clinical laboratory tests defined in the protocol operations manual (e.g., hematology and clinical chemistry) will be summarized.

For the analysis of laboratory data, values observed up to 30 days after the last dose of study drug will be included.

Each laboratory variable will be summarized for all time points (starting with baseline) with the number of non-missing observations, mean and standard deviation, median, minimum and maximum.

For continued groups, mean change from baseline to each applicable post-baseline visit will be summarized for selected laboratory variables, with the number of observations, baseline mean, and visit mean. The change from baseline mean, standard error, and 95% confidence interval will be presented for the mean change from baseline within each treatment group and difference between treatment groups.

Shift tables will be provided for each hematology, clinical chemistry parameter. Shifts from Baseline to the following endpoints will be considered: post-Baseline value and final value. This analysis will be performed only for category of "low or normal" at Baseline which shift to 'high' and category of "high or normal" at Baseline which shift to category of 'low.'

For selected laboratory variables including hemoglobin, neutrophils, lymphocytes, platelets, leukocytes, creatinine, ALT, AST, bilirubin, CPK, a listing of all observations collected will be generated for subjects that had at least one post-baseline observation meeting pre-defined criteria for potentially clinically important values. The number and percentage of subjects in each treatment group who have at least one post-baseline observation meeting the pre-defined criteria for potentially clinically important values will be provided for each variable. The criteria for potentially clinically important laboratory values will be determined by NCI CTCAE version 4.03 of greater than Grade 3 or greater than Grade 4.

For the purpose of assessing for potential Hy's law cases, the frequencies and percentages of subjects with post baseline liver-specific function test values that meet the following criteria of potential clinical interest will be summarized by treatment group for both short-term and long-term analyses:

- $ALT \geq 3 \times ULN$
- $ALT \geq 5 \times ULN$
- $ALT \geq 10 \times ULN$
- $ALT \geq 20 \times ULN$
- $AST \geq 3 \times ULN$

- $AST \geq 5 \times ULN$
- $AST \geq 10 \times ULN$
- $AST \geq 20 \times ULN$
- $TBL \geq 2 \times ULN$
- Alkaline phosphatase $\geq 1.5 \times ULN$
- ALT and/or AST $> 3 \times ULN$ and TBL $> 1.5 \times ULN$
- ALT and/or AST $> 3 \times ULN$ and TBL $> 2 \times ULN$

A listing of possible Hy's Law cases, defined as those who meet all of the following conditions at any post-baseline visit will be provided: ALT $> 3 \times ULN$ or AST $> 3 \times ULN$ and Total Bilirubin $\geq 2 \times ULN$.

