7.4 Statistical Analyses for Safety

Safety analyses will be carried out using the Safety Analysis Set, which includes all subjects who receive at least 1 dose of study drug. Subjects will be grouped to the treatment actually received. Safety will be assessed by AEs, physical examination, laboratory assessments, ECGs, and vital signs. Frequency tables and lists of subjects with treatment-emergent adverse events (TEAEs) by preferred term as in the Medical Dictionary for Regulatory Activities (MedDRA®) dictionary, by system organ class, by severity, and by relationship to the study drug as assessed by the Investigator will be provided. The changes from Baseline in vital signs, physical examination results, and clinical laboratory values will be analyzed in a descriptive manner. Shift of laboratory values from Baseline to defined time points will be tabulated. Pre-treatment AEs will be summarized separately.

All TEAEs, SAEs, AEs leading to discontinuation, and AESI will be collected during the study. A TEAE is defined as an event with onset or worsening after the first study dose of study drug and within 30 days after the last dose of study drug administration. The number and percentages of subjects experiencing TEAEs will be tabulated using the MedDRA system organ class and preferred term. Summaries (including percentages and event per 100 patient-year) of SAEs, deaths, AEs leading to discontinuation, and AESI will be provided as well. For selected laboratory and vital signs parameters, mean change from Baseline and percentage of subjects with evaluations meeting pre-defined criteria for Potentially Clinically Important values will be summarized.

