* Note: In the event the study is partially terminated, terminated groups will be removed from the comparison.

The binary secondary endpoints will be analyzed using the same approach as that for primary endpoint as specified in Section 8.4.2. Specifically, CMH adjusting for randomization stratification factors will be used to construct the treatment difference, the associated 95% CI and p-value between treatment group comparison. The NRI-C will be the primary approach for missing data handling in the analyses of binary secondary efficacy endpoints.

All continuous endpoints will be evaluated through the change from Baseline. For continuous endpoints with multiple post-Baseline visits, the treatment effect will be assessed through Mixed-effect Model Repeated Measures (MMRM) with treatment, visit

and treatment-by-visit interaction, randomization stratification factors, and the continuous fixed covariate of baseline measurement. An unstructured variance covariance matrix will be used. For continuous endpoints with a single post-baseline visit, the treatment effect may be assessed through analysis of covariance (ANCOVA) with baseline value, treatment, and randomization stratification factors as covariates. In addition, the descriptive statistics for continuous variables will be provided including sample size, mean, standard deviation, median, minimum and maximum.

For the count endpoint (e.g., number of flares by SLENAI SFI), negative binomial regression model will be used to assess treatment effect with treatment, and randomization stratification factors as covariates.

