9.0 Safety Analyses

9.1 General Considerations

Safety analyses will include reporting of adverse events, laboratory, and vital signs measurements. Safety analyses will be carried out using the Safety Analysis Set for both continued and terminated groups except for mean change from baseline analysis of laboratory and vital signs, which will be provided for continued groups only.

All summaries of adverse events will be provided using data through Week 24, through Week 48 and through Week 48 per 100 patient-years.

The following summary statistics will be presented for subjects who have both baseline and post-baseline values for laboratory parameters and vital signs: the mean value at baseline and at each respective protocol specified visit, and the mean, standard deviation and median for changes from baseline. Categorical data will be summarized using frequencies and percentages. The number of non-missing values will be given.

For the safety analyses, subjects are assigned to a treatment group based on the treatment actually received, regardless of the treatment randomized. A subject's actual treatment will be determined by the most frequent dose regimen received.

For the safety analyses, baseline is defined as the last measurement prior to the first dose of study drug.

Missing safety data will not be imputed.

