9.4 Analysis of Vital Signs

Vital sign measurements of systolic and diastolic blood pressure, pulse rate, body temperature, and weight will be summarized.

For the analysis of vital sign data, values observed up to 30 days after the last dose of study drug will be included.

Each vital sign variable will be summarized for all time points (starting with Baseline) with the number of non-missing observations, mean and standard deviation, median, minimum and maximum.

For continued groups, mean change from baseline to each applicable post-baseline visit will be summarized for each vital sign variable, with the number of observations, baseline mean, and visit mean. The change from baseline mean, standard error, and 95% confidence interval will be presented for the mean change from baseline within each treatment group and difference between treatment groups.

Vital sign variables will be evaluated based on potentially clinically important (PCI) criteria ([Appendix C](#)). For each vital sign PCI criterion, the number and percentage of subjects who have a vital sign value meeting the criteria will be summarized. Listings

will be provided to summarize subject-level vital sign data for subjects meeting PCI criteria.

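### SAP 9.3 and 9.4 specify no baseline covariate for between-arm differences in laboratory and vital-sign change, so the intervals are valid but on average wider than needed

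*SAP*

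**What the plan says.** SAP 9.3 sets the scope for laboratory data: "For continued groups, mean change from baseline to each applicable post-baseline visit will be summarized for selected laboratory variables". The display has the number of observations, the baseline mean and the visit mean. For the change itself, the SAP adds a mean, a standard error and an interval: a "95% confidence interval will be presented for the mean change from baseline within each treatment group and difference between treatment groups". SAP 9.4 repeats this for vital signs, where "mean change from baseline to each applicable post-baseline visit will be summarized for each vital sign variable". Neither section says how the between-group difference or its interval is calculated.

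The baseline value is available. In SAP 9.1, "baseline is defined as the last measurement prior to the first dose of study drug", and the summaries are limited to "subjects who have both baseline and post-baseline values for laboratory parameters and vital signs".

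For continuous efficacy endpoints the SAP does name a method. Sections 8.3 and 8.5.2 specify an MMRM with the baseline measurement as a continuous covariate. Where there is a single post-baseline visit, section 8.5.2 says the effect may be assessed by "analysis of covariance (ANCOVA) with baseline value, treatment, and randomization stratification factors as covariates".

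Protocol 7.4 sets the status of the safety analyses: "The changes from Baseline in vital signs, physical examination results, and clinical laboratory values will be analyzed in a descriptive manner".

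**The concern.** A difference in mean change fixes the slope on baseline at 1. ANCOVA estimates that slope. When the true slope is below 1, the change score has two drawbacks:

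- It adds baseline noise to the contrast, so the interval is wider than it need be.
- It passes part of any chance baseline difference between the arms into the estimate, with the opposite sign.

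With a planned 65 subjects per arm, and fewer at later visits, some imbalance is to be expected over several variables, visits and arm pairs. It can make a change look slightly larger or smaller than it is. Safety and the choice of dose(s) are both in the main objective (SAP 2.1), and the SAP chose to print between-arm intervals, which readers will use as comparisons. The information needed to sharpen them is already in the dataset.

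**Working it through.** **The plan's own figure.** The only design calculation in the documents is power for the primary endpoint (SAP 2.4, Protocol 7.7): 65 per arm, 25% placebo response, two-sided alpha of 0.10, and 78% to 91% power for differences of 20 to 25 points. With pooled variance under the null:

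- 20 points: (0.20 − 1.645 × 0.0837) / 0.0818 = 0.762, power 77.7%.
- 25 points: (0.25 − 1.645 × 0.0849) / 0.0820 = 1.345, power 91.1%.

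The stated range reproduces. It has no bearing on the safety intervals except that it supplies n = 65.

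**Inputs for the safety intervals.** n = 65 per arm comes from SAP 2.4. The baseline-to-visit correlation r and the SDs are not in the documents, so they are assumptions shown over a range.

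**Interval width with equal SDs.** In units of the baseline SD, the 95% half-widths are:

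- change score: 1.96 × √(2(1 − r)) × √(2/65)
- ANCOVA: 1.96 × √(1 − r²) × √(2/65)

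with √(2/65) = 0.175. The ratio, ANCOVA to change score, is √((1 + r)/2), which does not depend on n.

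| r (assumed) | Change score | ANCOVA | Ratio | Narrower by |
|---|---|---|---|---|
| 0.3 | 0.407 | 0.328 | 0.806 | 19.4% |
| 0.5 | 0.344 | 0.298 | 0.866 | 13.4% |
| 0.7 | 0.266 | 0.246 | 0.922 | 7.8% |
| 0.8 | 0.217 | 0.206 | 0.949 | 5.1% |
| 0.9 | 0.154 | 0.150 | 0.975 | 2.5% |

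A simulation with 65 per arm (1,000 trials per value of r, t-based least-squares intervals, so the degree of freedom spent on the covariate is counted) gave ratios of 0.870, 0.925 and 0.978 at r = 0.5, 0.7 and 0.9.

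**Unequal SDs.** If the follow-up SD is k times the baseline SD, the ratio is √(k²(1 − r²) / (1 + k² − 2rk)). At r = 0.5, 0.7 and 0.9:

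- k = 0.8: 0.756, 0.792 and 0.780
- k = 1.2: 0.933, 0.983 and 0.989

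The gain in these cases therefore runs from about 24% down to about 1%.

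**Chance imbalance.** The difference in baseline means between two arms has an SD of 0.175 baseline SD. An imbalance of 0.25 SD or more in either direction lies beyond 0.25/0.175 = 1.43 standard errors, which happens in about 15% of comparisons. With equal SDs the change score passes (1 − r) of the imbalance into the contrast:

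- r = 0.5: 0.5 × 0.25 = 0.125 SD, or 36% of the 0.344 half-width.
- r = 0.7: 0.3 × 0.25 = 0.075 SD, or 28% of 0.266.
- r = 0.9: 0.1 × 0.25 = 0.025 SD, or 16% of 0.154.

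**The case against.** The best defence is that nothing here is incorrect. Under randomization the difference in mean change is unbiased and its interval has proper coverage. Protocol 7.4 calls the analyses descriptive, and neither SAP section attaches a test or decision rule. The same parameters are also examined through shift tables, counts of potentially clinically important values, liver criteria, adverse events of special interest and unblinded DMC review. Baseline means are printed, so a reader can see an imbalance. The size of the gain cannot be fixed from the documents. ANCOVA also assumes a linear relation to baseline, which may suit skewed enzymes poorly, and an adjusted difference will not match the raw means beside it.

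Most of this stands, and it limits the point to an efficiency gain in descriptive output. It does not remove the point. Showing a baseline imbalance does not correct the contrast for it. A log scale deals with strongly skewed analytes, and a label deals with the mismatch in the table.

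A reader might infer more than the documents support:

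- **That the SAP adjusts for baseline values in all its efficacy models.** It does not. The CMH analyses of the primary and binary secondary endpoints, the negative binomial models for flares and the Cox model for time to flare use treatment and stratification factors, not a baseline value of the outcome. The comparison holds only for the continuous endpoints.
- **That the SAP states the safety differences are unadjusted.** It is silent on the method. Unadjusted is the natural reading, given the simple statistics in 9.1, but it is an inference.
- **That these intervals are how effects on hemoglobin, neutrophils, lymphocytes or creatinine will be judged.** That list belongs to the paragraph on potentially clinically important values in 9.3. The mean-change sentence speaks only of selected variables and does not list them.
- **That the absence of multiplicity control adds to the problem.** Baseline adjustment does not address multiplicity.

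**Conclusion.** The point holds as an inexpensive improvement to a valid descriptive analysis. SAP 9.3 and 9.4 specify no baseline covariate for a between-arm difference that they report with a 95% interval, although the baseline value is available for every subject in the summary and the SAP adjusts for it in its continuous efficacy models. Under equal SDs, adjustment narrows the interval by about 13% at r = 0.5, 8% at r = 0.7 and 2.5% at r = 0.9, and it largely removes the shift from chance baseline imbalance. The correlations and the equal-SD condition are assumptions, and the gain is negligible for variables that track their baseline closely. That adjustment never loses precision is a large-sample result under a common slope; in a single small dataset the gain is an average expectation.

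The documents do not support calling the planned intervals invalid or biased, or saying that a planned conclusion depends on them.

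**What to change.** In SAP 9.3 and 9.4, state that the between-arm difference at each visit will be estimated by ANCOVA with treatment and the baseline value, or by an MMRM with the same baseline covariate. It would be reported with a 95% CI and labelled as the baseline-adjusted difference. Say that strongly skewed analytes will be analysed on the log scale, and name the selected laboratory variables to which this applies. Keep the unadjusted within-arm means and their intervals as planned.

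The interim analysis has been done, so the change applies to later analyses.

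The cost is a sentence or two in each section and a standard procedure call. No new data are needed, no subject is lost, the analyses remain descriptive and no decision rule changes. The small downside is that the adjusted difference will not exactly equal the difference of the raw means shown in the table, which a footnote can explain. If the sponsor prefers the simple summary, the sections should at least say that the differences are unadjusted and descriptive.

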AbbVie may terminate this study prematurely at any time, either in its entirety or partially (discontinue 1 or more treatment groups), at any site. The study may be discontinued or terminated in case of an unacceptable risk, relevant toxicity, or a negative change in the benefit/risk assessment including the occurrence of AEs of which the character, severity, or frequency is new in comparison to the existing risk profile. In addition, data deriving from other clinical trials or toxicological studies which negatively influence the benefit/risk assessment might cause discontinuation or termination of the study. In the event the study is partially terminated, all subjects in the terminated arm(s) will be asked to return for a PD visit and to perform a 30-day follow-up phone call after the last dose of study drug. These subjects are not eligible for the LTE Study M20-186. The investigator may also stop the study at his/her site if he/she has safety concerns. If AbbVie terminates the study for safety reasons, AbbVie will promptly notify the investigator.

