9.2.4 Treatment-Emergent Adverse Events per Patient-Years of Exposure

Exposure-adjusted AEs through Week 48 per 100 patient-years will be provided, where AEs per 100 patient-years of exposure are defined as the number of AEs divided by the total exposure in 100 patient-years, i.e.,

$$100 * (\text{Number of TEAEs}) / (\text{Total Patient Years})$$

where total patient years is defined as the sum of the study drug exposure of all subjects, normalized by 365.25, and rounded to 1 decimal place. Note that one event per preferred

term per day per subject will be counted in the calculation of the number of AEs (i.e., a preferred term will not be counted twice on the same day for the same subject).

The TEAE through Week 48 per 100 patient-years will be provided for the following AE categories by SOC and PT:

- Any treatment-emergent AEs.
- Any COVID-19 related TEAEs.
- Any severe treatment-emergent AEs.
- Any serious treatment-emergent AEs.

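### If an arm is terminated after the interim, its final laboratory, liver and vital-sign threshold percentages are biased downward, because they take no account of monitored time

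*SAP*

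**What the plan says.** The threshold summaries count subjects who ever met a limit.

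- **Laboratory values.** For ten named variables, including CPK, SAP 9.3 plans "The number and percentage of subjects in each treatment group who have at least one post-baseline observation meeting the pre-defined criteria".
- **Liver thresholds.** The same section plans "the frequencies and percentages of subjects with post baseline liver-specific function test values" beyond each limit. These "will be summarized by treatment group for both short-term and long-term analyses", but neither period is defined.
- **Vital signs.** SAP 9.4 states that "the number and percentage of subjects who have a vital sign value meeting the criteria will be summarized".

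None of the three has a patient-year or time-to-event version.

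Three further provisions decide who is counted and for how long.

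- SAP 9.1: "Safety analyses will be carried out using the Safety Analysis Set for both continued and terminated groups". The only exception is mean change in laboratory values and vital signs, which is restricted to continued groups.
- Protocol 5.5: on partial termination, "all subjects in the terminated arm(s) will be asked to return for a PD visit". A phone call 30 days after the last dose follows.
- SAP 9.3: for laboratory data, "values observed up to 30 days after the last dose of study drug will be included". SAP 9.4 has the same rule for vital signs.

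Adverse events are treated differently. SAP 9.2.4 says "Exposure-adjusted AEs through Week 48 per 100 patient-years will be provided", and SAP 9.1 also cuts every adverse-event summary at Week 24 and at Week 48. Protocol 7.4 draws the same line: it gives rates for serious events, deaths, events leading to discontinuation and events of special interest, but only a percentage for potentially clinically important values.

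**The concern.** The chance of ever crossing a threshold grows with the time and the number of visits over which a subject is measured. A crude percentage is comparable between arms only if monitored time is similar. Terminating an arm breaks that condition. Its subjects leave early and stay in the same tables as subjects measured to Week 48. Without any termination, an arm with more early drug stops is affected in the same way: its subjects may keep attending visits, but values beyond 30 days after the last dose are left out.

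An arm may be terminated on benefit/risk grounds. Its laboratory signal would then be understated against placebo in the final tables, in a trial whose main objective covers safety and the choice of doses for further development.

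**Working it through.** **The plan's own figure.** The documents state no figure for these tables. The one design figure, 78% to 91% power, reproduces (77.7% and 91.1% with 65 per arm) but does not bear on this point.

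**Inputs from the documents**
- Full treatment period: 48 weeks (Protocol 4.1).
- Scheduled post-baseline laboratory visits: Weeks 2, 4, 8 and then every 4 weeks to 48, which is 13 visits (Protocol Appendix D). By Weeks 24, 32 and 40 there are 7, 9 and 11, plus the premature-discontinuation visit.
- Planned arm size: 65 (Protocol 7.7).
- Interim data cutoff for the first 50% of subjects: 7 July 2021 (SAP 11.2.1).

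**Assumptions.** A constant hazard of first crossing, and true 48-week risks r of 5%, 10% and 20%. Follow-up in a terminated arm is not documented, so a range of T weeks is shown.

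**Step 1: what the crude percentage shows.** Shown risk = 1 − (1 − r)^(T/48).

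| True 48-week risk | T = 24 | T = 32 | T = 40 |
|---|---|---|---|
| 5% | 2.5% | 3.4% | 4.2% |
| 10% | 5.1% | 6.8% | 8.4% |
| 20% | 10.6% | 13.8% | 17.0% |

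For example, 1 − 0.80^(24/48) = 10.6%. In an arm of 65 the expected count falls from 65 × 0.20 = 13 subjects to 65 × 0.106 = 6.9.

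**Step 2: how large a difference can be hidden.** Two arms show the same percentage when hazard × time is equal. An arm followed for T weeks therefore matches a fully followed arm when its hazard is 48/T times higher: 2.0, 1.5 and 1.2 times at 24, 32 and 40 weeks.

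**Step 3: which T is plausible.** 7 July 2021 minus 24 weeks is 20 January 2021, so the first half was randomised by about then, setting withdrawals aside. Assume a stop on 7 July or on 25 October 2021 (the protocol synopsis date). Assume also uniform accrual, with the first half randomised over 60 weeks and the second half between 20 January and the stop.
- Stop on 7 July: in the first half, 24/60 of subjects average 36 weeks and the rest have 48, giving 0.4 × 36 + 0.6 × 48 = 43.2. The second half averages 12. Mean: (43.2 + 12)/2 = 27.6 weeks.
- Stop on 25 October, 39.7 weeks after 20 January: the same calculation gives about 34 weeks.

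At 28 and 34 weeks a 20% risk shows as 1 − 0.80^(28/48) = 12.2% and 1 − 0.80^(34/48) = 14.6%. Averaging over the spread of follow-up instead of using the mean gives 11.8% and 14.2%.

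**Step 4: a fixed window alone is not enough.** Under the same assumptions 30% to 50% of the arm has under 24 weeks. A Week 24 percentage without censoring then shows 3.9% to 4.4% where 5.1% is expected (10% risk at 48 weeks).

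**Step 5: the rate scale.** For r = 10%, the first-event rate is −ln(0.90)/48 × 52.18 × 100 = 11.5 per 100 patient-years whatever T is. Simulated arms of 65 gave 11.5 with 24 weeks of follow-up and 11.4 with 48, against crude percentages of 5.2% and 10.0%.

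**The case against.** The strongest case against is that the reader is not left with crude percentages alone.

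- **Interim tables.** SAP 11.2.4 plans a summary of potentially clinically significant laboratory and vital-sign values in all arms. It uses cutoff dates that do not depend on arm, and it is done before that interim could stop any arm. Termination cannot bias it. This stands, but it leaves the final tables as they are.
- **Adverse-event rates.** Anemia, neutropenia, lymphopenia, renal dysfunction and hepatic disorders are events of special interest with patient-year rates. This stands in part. CPK, platelets and leukocytes are not on the SAP Appendix B list. CPK results are also withheld from sites (Protocol Table 4), and a laboratory abnormality becomes an adverse event only under the conditions in Protocol 6.1. A symptomless CPK rise may therefore appear only in the laboratory tables.
- **By-visit and exposure summaries.** SAP 9.3, 9.4 and 6.1 let a reader see that follow-up differs, and listings show the affected subjects. They do not adjust the percentages.
- **Liver periods.** The short-term version may supply a common window. It is undefined, and step 4 shows that a window without censoring still falls short.
- **Descriptive use.** No test or ratio is planned for these counts. That limits the harm, but arms shown side by side will be compared.

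Three stronger readings are tempting, and the documents do not support them.

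- A reader might infer that an arm has been stopped. Protocol 7.5 says the review committee decided which groups continue, but no document names a terminated arm or a date, and the SAP's wording is conditional.
- A reader might infer that a stopped arm must look safer than placebo, even at twice the true risk. At 16 weeks a 20% risk would indeed show as 7.2% against 10% on placebo. But a 16-week average needs the first half to stop exactly at Week 24 and the rest to average 8 weeks, (24 + 8)/2. At 24 to 40 weeks the shown ratio is 1.06 to 1.70: diluted from 2.0, not reversed.
- A reader might extend the point to QTcF. Seven of the eight post-baseline ECGs listed in SAP 9.6 fall by Week 24, and the premature-discontinuation visit includes one, so that count is little affected.

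**Conclusion.** The point holds in conditional form. If an arm is terminated, its final laboratory, liver and vital-sign threshold percentages are biased downward at equal hazard. More early drug stops in an arm have the same effect. The direction follows from the documents; the size rests on assumptions. With a constant hazard and mean follow-up of 24 to 40 weeks, a true 20% risk shows as 10.6% to 17.0%, or about 12% to 15% at the 28 to 34 weeks that the assumed dates suggest. Abnormalities that appear early in treatment would be understated less, and an arm with a high enough hazard would still look worse than placebo. The change is worth making because the sponsor already adjusts adverse events for exposure, and the other safeguards are weakest for CPK.

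**What to change.** - In SAP 9.3 and 9.4, add for all arms, beside each threshold percentage, the number of subjects with a first threshold event per 100 patient-years at risk, or a Kaplan-Meier estimate. Time should run to the first event or to the last included measurement.
- For any comparison that involves a terminated arm, add a version through Week 24 that censors subjects stopped earlier.
- Define the short-term period of the liver table as that same window, and define the long-term period too.

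The cost is SAP wording and a few table columns, with no new data. The rate assumes a roughly constant hazard; the Kaplan-Meier estimate does not. Both treat censoring as unrelated to risk. That is reasonable when a whole arm is stopped on one date, and less so when a subject stops drug because of a laboratory change.
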